## **Study Protocol with Statistical Analysis Plan**

### **Title: 3D X-Ray Motion Analysis of Ankle-Foot Motion After Total Ankle Arthroplasty**

#### **Objectives:**

- Quantify *in vivo* 3D ankle-foot kinematics through direct imaging of skeletal elements using high-speed dual-plane radiographic measurement using the Georgia Tech 3D X-ray Motion Analysis (XMA) system.
- Determine motion patterns of prosthetic components during clinically-relevant motions
- Evaluate extent that mobile bearing prostheses restore normal ankle motion in TAA patients
- Evaluate extent that fixed bearing prostheses restore normal ankle motion in TAA patients

#### **Design and Methods**

Quantifying motion within the ankle and foot is extremely challenging due to the inability to use external markers on the skin to accurately track the different bones and complex organization of joints. A high-speed biplanar X-Ray Motion Analysis (XMA) system (Imaging Systems & Service, Inc.) provides a direct method to obtain 3D radiographic images of skeletal motion. The XMA system includes two 45KW x-ray generators (EMD technologies), two 400KHU x-ray tubes (Varian), two 12" image intensifier tubes (Thales) and two XC-2M high-speed digital cameras (Xcitex). This system synchronizes the two x-ray beams with the opening and closing of the camera shutters to minimize radiation exposure and beam interference. Validated of the GT XMA System using phantom objects of known dimensions moving within the capture volume yielded an average measurement accuracy of 87 microns and an average measurement precision (reproducibility) was 73 microns.

Each participant will provide informed consent prior to enrolling in this study that is approved by the Georgia Tech Institutional Review Board (IRB). Each participant will undergo a CT scan to obtain a 3D digital model of their lower foot and ankle bones. In addition, they will participate in one data collection session to obtain X-Ray Motion Analysis (XMA) data.

The XMA system will be positioned around a walkway. Radiographic images will be gathered for each patient at 100 images per second and at a x-ray source to skin distance (SSD) greater than 100cm. The x-ray technique proposed for this study has already been verified and approved by the Georgia Tech Office of Radiological Safety (ORS) to generate effective radiation doses within allowable, safe limits for live human studies. During the XMA session, participants will be imaged in three conditions:

1. Assuming a neutral standing position to establish reference coordinate axes
2. Rotating their ankle in a non-weight-bearing position to obtain active range of motion measurements
3. Walking at a preferred speed to obtain ankle-foot kinematics during gait

Parameters for each procedure include:

- Each patient will maintain an SSD of at least 100cm from the x-ray emitter.
- Duration of each trial will not exceed 6 seconds, at 100 frames per second.
- Multiple trials may be performed to ensure the patient's ankle joint is recorded within the video capture volume.
- Multiple trials/condition will be used for analysis, not to exceed 30 trials in total
- Patient radiation exposure will <30 rem (10% of exposure required for any skin irritation)

The motion analysis procedure is marked by patient data collection, tracking, and reanimation for joint kinematics. In post-processing, sagittal, coronal, and axial plane motion of the implanted ankle prosthesis will be tracked using x-ray motion analysis software (XROMM Autoscooper, Providence RI) for all components of the total ankle replacement. Once CT scan data are obtained for each enrolled study participant, 3D bone surface models will be generated (3D Slicer) for all participants. These bone surface models will be used along with the x-ray video data to calculate joint angle trajectories and joint ranges of motion during plantar/dorsiflexion, internal/external rotation, and inversion/eversion of the foot-ankle complex using 3D animation software (Maya, Autodesk).

#### Statistical Analysis Plan

We will use a repeated measure design to test against the null hypothesis that participants that have a particular prosthetic ankle implant do not exhibit a difference in ankle joint range of motion compared to healthy, age- and gender-matched controls. Participants will be enrolled into a group that have experienced total ankle arthroplasty and currently have a mobile bearing (Stryker STAR) prosthetic implant. Age- and gender-matched participants that have experienced total ankle arthroplasty and currently have a fixed bearing 2-component implant (INBONE 2 Total Ankle System) will be enrolled into another group. Healthy, age- and gender-matched participants with intact ankle joints will be recruited into a control group. A comparison will be made between the mobile bearing implant group and the matched control group using a paired, one-tailed t-test. A second comparison will be made between the fixed bearing implant group and the matched control group using a paired, one-tailed t-test. Available x-ray-based gait kinematics data on intact subjects (Wang et al. 2015) were used to perform a power analysis (G\*Power statistical software) to determine that a sample size of 5 participants per group is needed to distinguish differences between group means with a Bonferroni-corrected alpha level of 0.025 and a power of 0.95.

Reference: Wang, B., Roach, K.E., et al., Accuracy and feasibility of high-speed dual fluoroscopy and model-based tracking to measure in vivo ankle arthrokinematics. *Gait & Posture*. 41(2015) p. 888-893.

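### The flat Bonferroni level of 0.025 for the two implant-versus-control tests is valid, but Holm's step-down rule would keep the same family-wise error and reject at least as much, for one added SAP sentence.

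*Combined protocol and SAP*

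**What the plan says.** The Statistical Analysis Plan section of the combined document defines two tests. For the mobile bearing implant: "A comparison will be made between the mobile bearing implant group and the matched control group using a paired, one-tailed t-test". For the fixed bearing implant: "A second comparison will be made between the fixed bearing implant group and the matched control group using a paired, one-tailed t-test". Neither sentence gives a significance level.

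The level appears only in the sizing sentence, which states that "a sample size of 5 participants per group is needed to distinguish differences between group means" and continues "with a Bonferroni-corrected alpha level of 0.025 and a power of 0.95". The basis is described as "Available x-ray-based gait kinematics data on intact subjects", with no effect size or standard deviation. The controls are described once ("Healthy, age- and gender-matched participants with intact ankle joints will be recruited into a control group"), so one control group appears to serve both comparisons. No step-down rule and no family-wise level is stated; 0.05 is inferred from 0.025 × 2.

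**The concern.** Bonferroni holds each test at 0.025 whatever the other one shows. Holm tests the smaller p-value at 0.025 and, once that is significant, allows the larger one 0.05. It protects the family-wise error under the same conditions. With 5 pairs there are only 4 degrees of freedom, and the two critical values are far apart: t = 2.776 at 0.025 and 2.132 at 0.05. An implant whose test statistic falls between them would be declared not significant under the flat rule even when the other implant is clearly different from controls.

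The Objectives pose a separate question for each bearing type, so the second comparison matters in its own right. Each participant has a CT scan and up to 30 x-ray trials, which is a reason to get as much as possible from the planned 15 people (3 groups of 5).

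**Working it through.** **Inputs from the SAP.** Two paired one-tailed t-tests; n = 5 pairs each, so 4 degrees of freedom; level 0.025; power 0.95, read as per comparison.

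**Assumptions, not in the documents.** The effect size dz (mean paired difference divided by its standard deviation), and the correlation between the two sets of paired differences. The correlation is taken as 0 and as 0.5; the latter is what a shared control with equal variances gives.

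**1. The plan's own figures.** 0.05 / 2 = 0.025 is exact. If the tests were independent, the family-wise error would be 1 − (1 − 0.025)² = 0.0494; it can never exceed 0.05. The sample size of 5 cannot be reproduced without an effect size, so the power equation is solved backwards:

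power = P(T > t_crit), with T noncentral t, df = n − 1, noncentrality dz·√n.

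- n = 5 reaches 0.95 at level 0.025 when dz = 2.204 (noncentrality 2.204 × √5 = 4.93).
- n = 4 would already reach 0.95 when dz = 2.827.

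A stated requirement of 5 therefore fits dz from about 2.20 to 2.83.

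**2. Where the rules differ.** They give different results only when one p-value is at most 0.025 and the other lies between 0.025 and 0.05. Otherwise the conclusions are identical.

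**3. Gain with equal effects.** Let b be the power at 0.025 and a the power at 0.05. For independent tests:

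- Bonferroni: per test b; both b².
- Holm: per test b + (a − b)·b; both b² + 2b(a − b).

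At dz = 2.204, b = 0.950 and a = 0.9894. Holm per test is 0.950 + 0.0394 × 0.950 = 0.9875. Both significant is 0.9025 under Bonferroni and 0.9025 + 2 × 0.950 × 0.0394 = 0.977 under Holm. Simulation with 1,000,000 replicates confirms this and supplies the results at correlation 0.5. Ranges below run over correlations 0 and 0.5.

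| True dz, both implants | Per test, Bonferroni | Per test, Holm | Both, Bonferroni | Both, Holm |
|---|---|---|---|---|
| 2.83 | 0.995 | 0.999 to 0.9996 | 0.990 to 0.991 | 0.999 |
| 2.20 | 0.950 | 0.983 to 0.988 | 0.90 to 0.91 | 0.975 to 0.977 |
| 1.65 (0.75 × 2.20) | 0.787 | 0.871 to 0.886 | 0.62 to 0.66 | 0.82 |
| 1.5 | 0.71 | 0.80 to 0.82 | 0.51 to 0.55 | 0.72 to 0.74 |

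**4. What does not change.** At dz 2.20 the chance of at least one significant result is 0.998 (correlation 0) or 0.991 (correlation 0.5) under either rule. If only one implant differs (dz 2.20 and 0), power for the real effect goes from 0.950 to 0.951 at most.

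**5. Error rates.** With both nulls true, the family-wise error is the same for both rules: 0.049 at correlation 0 and 0.047 at 0.5. With one real effect of dz 2.20, the error on the true-null comparison is 0.025 under Bonferroni and 0.049 to 0.050 under Holm.

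**6. Sample size.** At dz 2.20, 4 pairs under Holm give 0.925 per test, so Holm saves no participant.

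**The case against.** The strongest reply is that nothing here is wrong. Bonferroni controls the error, and the 0.95 power is claimed at 0.025, so the design meets its own target without Holm. That stands.

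A reader might infer that power is being given away for nothing. The figures do not support that. When one implant truly differs, Holm roughly doubles the chance of wrongly declaring a difference for the other, from 0.025 to 0.05, though the family-wise error stays within 0.05. Bonferroni also supplies simple simultaneous confidence limits that agree with the tests. The Objectives ask about the extent of restored motion, for which intervals would be natural, although the SAP plans none.

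A reader might also infer that the study fails unless both tests reject, and so treat 0.90 to 0.91 as its real power. The documents set no such criterion: the objectives are separate, and one significant and one non-significant comparison would still answer both. The 'both' columns above describe the procedures, not a success rule of the plan.

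Two further limits stand. Using 0.025 as the decision level is a reading of the sizing sentence, not an explicit rule. And the SAP names no single range-of-motion outcome, although non-weight-bearing and walking conditions and three motion directions are planned, so the family may prove larger than two. Holm extends to more tests, but the family must be fixed first.

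**Conclusion.** The point holds as an optional efficiency gain, not as a defect. That Holm rejects at least as much as Bonferroni at the same family-wise 0.05 follows from the method and needs no assumption about effects or correlation.

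The size of the gain does rest on assumptions: equal effects, correlation 0 to 0.5, and an effect size the documents do not give. Within the range that fits the planned 5, per-comparison power rises by 3.3 to 3.8 percentage points at the lower end (dz 2.20) and by under half a point at the upper end (dz 2.83). It rises by about 9 to 11 points if the true dz is 1.5, a value chosen for illustration only. A smaller effect than planned cannot be excluded, since the power analysis used data on intact subjects. If only one implant differs from controls, the gain is about 0.1 point or less.

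**What to change.** Add one sentence to the Statistical Analysis Plan, before results are seen: the two p-values are ordered, the smaller is tested at 0.025 and, only if it is significant, the larger is tested at 0.05, for a family-wise level of 0.05. This also makes the decision rule explicit, which the present text does not.

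Keep 5 per group, and word the power statement as 0.95 per comparison at the 0.025 level. Holm's first step uses that level, so the sizing stays conservative.

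The change needs no extra participants, data or analysis work. The statistical price is the higher error on a true-null second comparison and the loss of simple matching simultaneous limits. If the sponsor prefers Bonferroni for those reasons, a sentence saying that both tests are judged at 0.025 is an acceptable alternative.
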